8.4.3.2. Unsteadiness and Sensory Evaluation

Assessment of unsteadiness and peripheral sensation will be evaluated by interview and assessment of vibratory sensation with a tuning fork applied to the lateral side of the right and left ankle. The following will be evaluated at each visit;

- Numbness: present/absent (if present record severity)
- Unsteadiness (eg, unsteadiness/dizziness; standing/sitting): present/absent (if present record severity)
- Vibratory sensation (with a tuning fork applied to the lateral side of the right and left ankles) with a tuning fork: Seconds (measure time of vibration that is felt when the handle of a vibrating 128 Hz [tuning fork is put against the outer ankle])

If present, the severity will be graded on the following 3-point scale;

- Mild: The event does not interfere with activities of daily living.
- Moderate: The event interferes to some extent with activities of daily living.
- Severe: The event interferes significantly with activities of daily living.

8.4.3.3. Columbia Suicide Severity Rating Scale (C-SSRS)

The C-SSRS is a clinician-rated instrument that captures the occurrence, severity, and frequency of suicide-related ideations and behaviours during the assessment period.

Suicidal ideation is classified on a 5-item scale: 1 (wish to be dead), 2 (nonspecific active suicidal thoughts), 3 (active suicidal ideation with any methods [not plan] without intent to act), 4 (active suicidal ideation with some intent to act, without specific plan), and 5 (active suicidal ideation with specific plan and intent). The C-SSRS also captures information about the intensity of ideation, specifically the frequency, duration, controllability, deterrents, and reasons for the most severe types of ideation. Suicidal behavior is classified on a 5-item scale: 0 (no suicidal behavior), 1 (preparatory acts or behavior), 2 (aborted attempt), 3 (interrupted attempt), and 4 (actual attempt). More than 1 classification can be selected provided they represent separate episodes. For actual attempts only, the actual or potential lethality is classified for the initial, most lethal, and most recent attempts. C-SSRS will be evaluated at screening, baseline, Week 4, Week 12, Week 24, and Week 48.

The sever level of suicidal ideation 5 items from low to high:

- 1: Wish to be dead
- 2: Non-specific active suicidal thoughts
- 3: Active suicidal ideation with any methods (not plan) without intent to act
- 4: Active suicidal ideation with some intent to act, without specific plan
- 5: Active suicidal ideation with specific plan and intent

The sever level of suicidal behavior 5 items from low to high:

- 1: Preparatory Acts or Behavior
- 2: Aborted Attempt
- 3: Interrupted Attempt
- 4: Actual Attempt
- 5: Suicidal Behavior

8.4.3.4. Laboratory Tests

Hematology tests will include: Red blood cell count, hemoglobin, hematocrit value, white blood cell count, sedimentation rate, c-reactive protein and platelet count.

Blood Chemistry will include: Albumin , Total protein, aspartate aminotransferase (AST), alanine aminotransferase (ALT), lactate dehydrogenase (LDH), alkaline phosphatase (ALP), sed rate , c-reactive protein (CRP) ,total bilirubin, direct bilirubin, creatine kinase (CK), total cholesterol, triglycerides, blood urea nitrogen (BUN), bicarbonate, serum glucose , serum creatinine level, uric acid, sodium (Na), potassium (K), chloride, calcium (Ca) and Vitamin B6.

Note: In addition, GGT will be obtained in only Japan country.

Qualitative urinalysis will include: Protein, glucose, occult blood, white blood cells, urobilinogen, and bilirubin.

Pregnancy test: For female subjects only, serum beta-human chorionic gonadotropin (hCG) level or urine dipstick will be conducted.

Laboratory values below the limit of quantification

Laboratory values below 1/2 LLOQ (lower limit of quantification) will be used for BLQ (below the limit of quantification) for data summary statistics.

Handling of Reference Values and Indeterminate Values for Clinical Laboratory Test Parameters

If laboratory test value or its reference is indeterminate due to a problem with the test sample,

then this value will be handled as a missing value.

Criteria for Potentially Clinically Significant Values (PCSV for laboratory):

The following criteria will be defined ^{8,9}

Chemistry

- ALT $\geq 3 \times$ Upper Limit of Normal Range (ULN), $5 \times$ ULN, $10 \times$ ULN, $20 \times$ ULN
- AST $\geq 3 \times$ ULN, $5 \times$ ULN, $10 \times$ ULN, $20 \times$ ULN
- ALT and/or AST $\geq 3 \times$ ULN, $5 \times$ ULN, $10 \times$ ULN, $20 \times$ ULN
- Total Bilirubin $\geq 2 \times$ ULN
- ALP >400 U/L
- ALT or AST $> 3 \times$ ULN with Total Bilirubin $> 1.5 \times$ ULN
- ALT or AST $> 3 \times$ ULN with Total Bilirubin $> 2 \times$ ULN
- Hy's law (ALT or AST $> 3 \times$ ULN and ALP $< 2 \times$ ULN and Total Bilirubin $\geq 2 \times$ ULN)
- LDH $\geq 3 \times$ ULN
- BUN ≥ 30 mg/dL
- Serum Creatine ≥ 2.0 mg/dL
- Uric acid Male >10.0 mg/dL, Female >8.0 mg/dL
- CK $\geq 3 \times$ upper limit of normal
- Chloride (Low) ≤ 90 mEq/L
- Chloride (High) ≥ 118 mEq/L
- Potassium (K) (Low) <3.0 mmol/l
- Potassium (K) (High) >5.5 mmol/l
- Sodium (Na) (Low) <130 mmol/l
- Sodium (Na) (High) ≥ 150 mmol/l
- Calcium (Ca) (Low) <7.0 mg/dL
- Calcium (Ca) (High) ≥ 12 mg/dL
- Concurrent Hepatic Abnormality:
 - ALT or AST $> 3 \times$ ULN with Total Bilirubin $> 1.5 \times$ ULN
 - ALT or AST $> 3 \times$ ULN with Total Bilirubin $> 2 \times$ ULN
 - Hy's law (ALT or AST $> 3 \times$ ULN and ALP $< 2 \times$ ULN and Total Bilirubin $\geq 2 \times$ ULN)

Hematology

- Hematocrit:
 - Male $\leq 37\%$ and decrease of ≥ 3 percentage points from baseline,
 - Female $\leq 32\%$ and decrease of ≥ 3 percentage points from baseline
- Hemoglobin:

Statistical Analysis Plan
Protocol No. MT-1186-A02

Mitsubishi Tanabe Pharma America, Inc.

- Male \leq 11.5 g/dL,
- Female \leq 9.5 g/dL
- White blood count (Low) \leq 2800/mm³
- White blood count (High) \geq 16,000/mm³
- Neutrophils Absolute count $<$ 1,000/mm³
- Platelet count (Low) \leq 100,000/mm³
- Platelet count (High) \geq 700,000/mm³

8.4.3.5. 12-Lead ECG

A 12-lead ECG will be performed after the subject has rested for at least 5 minutes in a supine position. The ECG will include the following numerical measurements: HR, R wave to R wave (RR) interval, heart rate, QRS, QT, QTcB, and QTcF. The Investigator will perform an overall evaluation of the ECG for safety purposes and the recording will be reported as 'normal', 'abnormal CS', or 'abnormal NCS'

The RR, QTcF and QTcB will be calculated using the below formulas, regardless of performed in CRF.

- RR (msec) will be calculated as $\{60 / \text{heart rate (beats/min)}\} * 1000$ and reported to integer.
- QTcF (msec) and QTcB (msec) will be calculated as $\{QT (\text{sec}) / RR (\text{sec}) ^ {(1/3)}\} * 1000$ and $\{QT (\text{sec}) / RR (\text{sec}) ^ {(1/2)}\} * 1000$ respectively and reported to integer.

Criteria for Potentially Clinically Significant Values (PCSV for 12-Lead ECG):

HR at post-baseline \leq 50 bpm and decrease from baseline \geq 20 bpm

HR at post-baseline \geq 120 bpm and increase from baseline \geq 20 bpm

QRS at post-baseline \geq 120 msec and QRS at baseline $<$ 120 msec

Baseline QTc \leq 450 msec and QTc $>$ 450 msec at post-baseline

Baseline QTc \leq 480 msec and QTc $>$ 480 msec at post-baseline

Baseline QTc \leq 500 msec and QTc $>$ 500 msec at post-baseline

Change from baseline at post-baseline in QTc $>$ 30 msec

Change from baseline at post-baseline in QTc $>$ 60 msec

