#### 8.2.1 Risk/Benefit Assessment

Edaravone has been evaluated in 6 Phase 1 studies in healthy subjects in Japan and Europe and has been evaluated in other clinical studies, including ALS, as follows:

- 8 clinical studies in acute ischemic stroke (AIS) subjects in Japan and Europe with IV edaravone;
- 3 clinical studies in subarachnoid hemorrhage subjects in Japan with IV edaravone;
- 5 clinical studies in ALS subjects in Japan with IV edaravone; and
- 7 clinical studies with oral edaravone.

The treatment of AIS and ALS in Japan states that IV edaravone (MCI-186) is contraindicated in subjects with severe renal impairment and should be administered with care in subjects with hepatic impairment. Conversely, there are no contraindications or warnings to subjects with renal or hepatic impairment in the United States Package Insert (USPI) for treatment of ALS in the US.

In the USPI (IV edaravone) Warnings and Precautions Section, hypersensitivity reactions (redness, wheals, and erythema multiforme) and cases of anaphylaxis (urticaria, decreased blood pressure, and dyspnea) have been reported in spontaneous postmarketing reports with edaravone. Edaravone contains sodium bisulfite, a sulfite that may cause allergic type reactions, including anaphylactic symptoms and life-threatening or less severe asthmatic episodes in susceptible people. The overall prevalence of sulfite sensitivity in the general population is unknown. Sulfite sensitivity occurs more frequently in asthmatic people.

In the USPI (IV edaravone) adverse reactions section, the most common adverse reactions observed during clinical studies were contusion, gait disturbance, headache, dermatitis, eczema, respiratory failure, respiratory disorder, hypoxia, glycosuria, and tinea infection.

Risk related to COVID-19 was also assessed. Edaravone is not known to alter immune function. However, there may be additional risk to participants due to exposure to COVID-19 during study related visits (dependent on the country/region conditions). Subjects will be encouraged to observe social distancing, wear face masks/coverings and avoid social gatherings during the conduct of the clinical trial and site visits, as long as COVID-19 is prevalent. Additionally, the Sponsor will monitor country conditions and prepare contingency plans for COVID-19 related restrictions that may prevent site visits.

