# 13.7.2 Blood Chemistry

Albumin, total protein, AST, ALT, lactate dehydrogenase, alkaline phosphatase (ALP), creactive protein, total bilirubin, direct bilirubin, creatine kinase, total cholesterol, triglycerides, blood urea nitrogen, bicarbonate, serum glucose, serum creatinine level, uric acid, sodium (Na), potassium (K), chloride, calcium (Ca), and cystatin C. Vitamin B6 will be measured at the time points described in Table 1.

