#### Vital Signs

Vital signs (sitting systolic/diastolic blood pressure, orthostatic hypotension, heart rate, respiratory rate, and axillary, oral, temporal [skin-based], or tympanic body temperature) will be descriptively summarized for values and the changes from baseline at each visit.

For evaluation ("Normal/abnormal CS/abnormal NCS") by the Investigator in vital signs, a shift table of the change from baseline will be summarized at each visit by treatment group.

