#### **Clinical Laboratory Assessments**

Clinical laboratory tests described in the Section 13.7 will be descriptively summarized for values and the changes from baseline at each visit by each treatment group. For urinalysis parameters, shift tables will be prepared for each visit, and category by treatment group.

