- g. A 12-lead ECG will be performed after the subject has rested for at least 5 minutes in a supine position. The ECG must include the following measurements: R wave to R wave interval, heart rate, QRS, QT, QTcB, and QTcF. The Investigator will perform an overall evaluation of the ECG for safety purposes and the recording will be reported as 'normal', 'abnormal clinically significant (CS)', or 'abnormal not clinically significant (NCS)'. Abnormalities of clinical significance will be reported as AEs. Repeat measurements will be performed¹ if needed.
- h. To be calculated by the Sponsor.
 - i. Events are time to death, tracheostomy, or permanent assisted mechanical ventilation (≥ 23 hours/day). If subject discontinues treatment, sites must follow-up with phone calls at Weeks 24, 36, and 48.
 - j. Will be drawn at the same times as the biomarkers. The additional biomarkers sampling will be performed at selected study sites where local regulations and IECs allow.
 - k. At selected sites, Investigator (or Sub-I) will measure the parameters Compound Muscle Action Potential (CMAP), Motor Unit Number Index (MUNIX), Sensory Nerve Action Potential (SNAP), and Sensory Nerve Conduction Velocity (SNCV).

Statistical Analysis Plan
Protocol No. MTT-1186-A02

1. To include: red blood cell count, hemoglobin, hematocrit value, white blood cell (WBC) count with differential, and platelet count.
2. To include: albumin, total protein, aspartate aminotransferase (AST), alanine aminotransferase (ALT), lactate dehydrogenase (LDH), alkaline phosphatase (ALP), c-reactive protein, total bilirubin, direct bilirubin, creatine kinase (CK), total cholesterol, triglycerides, blood urea nitrogen (BUN), bicarbonate, serum glucose, serum creatinine level, uric acid, sodium (Na), potassium (K), chloride, calcium (Ca) and cystatin C.
3. To include protein, glucose, occult blood, WBCs, urobilinogen, and bilirubin.

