9.3.4. Vital Signs

Vital sign measurements and their change from baseline will be listed and summarized using descriptive statistics by visit up to week 48. Those parameters will include: heart rate (HR), supine and standing blood pressure (BP) (both systolic and diastolic), body temperature and weight. Furthermore, orthostatic vital sign and supine minus standing blood pressure (both systolic and diastolic) and their change from baseline will be summarized with descriptive statistics by visit.

Vital sign values will be considered PCSV if they meet both criteria of the observed value and the change from baseline listed in section 8.4.3.6. The number and percentage of subjects with PCSV at any time post-baseline will be tabulated. The percentages will be calculated from the number of subjects with a baseline value and any time post-baseline value. The number and percentage of subjects with orthostatic hypotension as defined in section 8.4.3.6 will be summarized in the same way.

9.3.5. 12-Lead ECGs

All ECGs parameters will be listed and analyzed.

The ECGs will be assessed by the investigator and deemed “Normal”, “Abnormal, not clinically significant” (Abnormal, NCS) and “Abnormal, clinically significant” (Abnormal, CS) and tabulated by visit up to week 48 using frequency counts and percentages.

In addition, the numerical ECG parameters and their change from baseline generated by the central ECG laboratory (see section 8.4.3.5) will be summarized by descriptive statistics for each parameter by visit.

ECG parameters values will be considered PCSV if they meet the criteria listed in section 8.4.3.5. The number and percentage of subjects with PCSV will be tabulated. The percentages are to be calculated from the number of subjects with available baseline values and any time post-baseline value for a specific category.

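### SAP 8.4.3.4 omits cystatin C and SAP 9.3.4 omits respiratory rate from the parameters to be analysed, against the protocol's promise to summarise both, and SAP Section 11 declares neither omission

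*SAP*

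**What the plan says.** **Cystatin C.** The chemistry panel in Protocol 13.7.2 ends with "serum creatinine level, uric acid, sodium (Na), potassium (K), chloride, calcium (Ca), and cystatin C". Protocol 17.4.5.9 then commits to analysing the panel: "Clinical laboratory tests described in the Section 13.7 will be descriptively summarized for values and the changes from baseline at each visit", by treatment group. In the SAP, the chemistry footnote to Table 1 (Section 4.1) still reads "uric acid, sodium (Na), potassium (K), chloride, calcium (Ca) and cystatin C", and the Japan schedule has the same analyte. The list in SAP 8.4.3.4 ends differently: "uric acid, sodium (Na), potassium (K), chloride, calcium (Ca) and Vitamin B6".

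**Respiratory rate.** The vital-signs paragraph of Protocol 17.4.5.9 promises by-visit descriptive summaries of values and changes for a list that includes "orthostatic hypotension, heart rate, respiratory rate, and axillary, oral, temporal [skin-based], or tympanic body temperature". SAP 3.3.4 names respiratory rate as a safety endpoint, and SAP 8.4.3.6 names it as a measurement. SAP 9.3.4, which states what will be summarised, gives heart rate, then "supine and standing blood pressure (BP) (both systolic and diastolic), body temperature and weight", then the orthostatic measures.

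**Precedence and declared changes.** SAP Section 2 says that its analysis details supersede the protocol's. SAP Section 11 declares two changes from the protocol: the physical-examination summary and the FAS definition.

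**The concern.** Two safety parameters are collected throughout, and the protocol promises a descriptive comparison of each. Neither appears where the SAP says what will be analysed. Because the SAP takes precedence, the protocol's promise does not restore them automatically. A programmer working from the named parameters could deliver tables without either, and nothing in Section 11 would show that anything had changed.

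Cystatin C has some weight here because the SAP's only kidney-function criteria for potentially clinically significant values (PCSVs) are BUN at or above 30 mg/dL and serum creatinine at or above 2.0 mg/dL. SAP Section 1 describes ALS as dominated by muscle atrophy and weakness. It is general physiology, not a statement in the documents, that creatinine is produced from muscle, so falling muscle mass tends to lower it whatever the kidney is doing. A second renal marker that the protocol already collects is therefore worth tabulating.

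Respiratory rate has a similar claim. Protocol 8.2.1 reports respiratory failure, respiratory disorder and hypoxia among the common adverse reactions in the US label for the IV product.

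**Working it through.** The plan gives no figure to reproduce here. The check is an item-by-item comparison of lists.

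**1. Chemistry.** Protocol 13.7.2 names 22 analytes: albumin, total protein, AST, ALT, LDH, ALP, CRP, total bilirubin, direct bilirubin, CK, total cholesterol, triglycerides, BUN, bicarbonate, glucose, creatinine, uric acid, sodium, potassium, chloride, calcium and cystatin C. Vitamin B6 is added in a separate sentence, at set visits.

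The chemistry list in SAP 8.4.3.4 has 23 entries: 21 of those 22, plus vitamin B6, plus sedimentation rate (21 + 1 + 1 = 23). The missing analyte (22 − 21 = 1) is cystatin C. Sedimentation rate appears in both the hematology and the chemistry lists of 8.4.3.4, but in neither 13.7.1 nor 13.7.2 of the protocol. The creatinine PCSV row is printed as creatine.

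**2. Vital signs.**

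| Parameter in Protocol 17.4.5.9 | SAP 3.3.4 endpoint | SAP 8.4.3.6 measurement | SAP 9.3.4 summary |
|---|---|---|---|
| Systolic/diastolic pressure | yes | yes | yes (supine and standing) |
| Orthostatic hypotension | yes | yes | yes |
| Heart rate | yes | yes | yes |
| Respiratory rate | yes | yes | **no** |
| Body temperature | yes | yes | yes |

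Respiratory rate is the only parameter with no counterpart in 9.3.4.

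**3. Declared changes.** Neither parameter is among the two entries in SAP Section 11.

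**4. Extent.** Protocol Table 1 and SAP 10.3 place both chemistry and vital signs at Weeks 4, 8, 12, 24, 36 and 48, which is six post-baseline visits. The exposed output is 2 parameters × 6 visits × 2 arms = 24 arm-by-visit summaries of value and change. The by-arm presentation follows from Protocol 17.3, which has safety endpoints analysed by treatment group.

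**5. Why a between-arm table is useful.** The regimens differ in planned active-drug days. Group 1 has 12 × 28 = 336. Group 2 has 14 + 11 × 10 = 124. The ratio is 336/124 = 2.7. Comparing safety between the regimens is the trial's secondary objective, and a subject-level listing does not give that comparison.

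**The case against.** The strongest reply is that these are loosely drafted lists, not decisions to drop anything. SAP 9.3.3 governs the laboratory outputs. It lists all laboratory data, summarises central-laboratory biochemistry with change from baseline by visit, and names no analytes. SAP 9.3.4 opens by saying that vital-sign measurements in general will be summarised. Section 8.4.3.4 is visibly imprecise in other ways: it puts CRP under two headings and omits the white-cell differential, yet sets a neutrophil criterion. The Table 1 footnotes still carry cystatin C. All of this stands, and it makes oversight the likely explanation. It does not settle which list a programmer should follow, and that is the defect.

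Three stronger readings are tempting, and the documents do not support them.

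- *A renal flag was removed.* Neither document ever had a cystatin C criterion or a post-baseline GFR criterion. GFR appears only as a screening exclusion. Low/normal/high shift tables, which cover creatinine and BUN, remain, as do the urinalysis shifts. Clinically significant laboratory abnormalities are recorded as adverse events (Protocol 15.5), and the IDMC periodically reviews unblinded safety data.
- *The creatinine criterion fires only after GFR has fallen below the entry limit of 30.* That depends on baseline values the documents do not give. Suppose creatinine varies inversely with GFR and baseline GFR is 90. A baseline creatinine of 0.6 then puts the trigger at 90 × 0.6/2.0 = 27, while 1.0 puts it at 90 × 1.0/2.0 = 45. The answer falls on either side of 30 according to the assumption, so nothing is claimed from it.
- *The protocol treats edaravone as a renal hazard generally.* Protocol 8.2.1 says that the IV product in Japan "is contraindicated in subjects with severe renal impairment" (severe impairment only), but goes on to say that the US label carries no renal contraindication or warning.

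**Conclusion.** The concern holds as an undeclared inconsistency in safety reporting. On a literal reading of SAP 8.4.3.4 and 9.3.4, two summaries promised by the protocol are lost: one of 22 chemistry analytes and one vital sign, each over six post-baseline visits in two arms. The SAP contradicts itself on both. A reader might infer that the sponsor chose to stop analysing cystatin C and respiratory rate. The text does not show that, since the SAP still names each of them in two other places.

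The size is modest. Collection does not change, the data remain in listings, other renal outputs remain, and neither the primary analysis nor the key secondary tests are touched. The textual part rests on no assumption. The argument that cystatin C deserves its own table rests on creatinine depending on muscle mass, which is general knowledge and not stated in the plan.

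**What to change.** - In SAP 8.4.3.4, add cystatin C to the chemistry list, remove sedimentation rate from both the hematology and the chemistry lists (the protocol does not collect it), and correct the PCSV row to serum creatinine.
- In SAP 9.3.4, add respiratory rate to the parameters summarised.
- Summarise both parameters as values and change from baseline, by visit and arm.
- If either omission is intended, declare and justify it in Section 11 instead.

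Optionally, add a descriptive by-visit summary of GFR using the same method as at screening. A new PCSV threshold for GFR is not part of this request: the protocol never promised one, and an entry criterion is not an on-study safety limit.

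The cost is a few lines of SAP text and a few table rows. No new samples, visits or data collection are needed.

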8.4.3.6. Vital Signs

The following measurements will be performed: sitting systolic and diastolic blood pressure, heart rate (eg, beats per minute), respiratory rate, and axillary, oral, temporal (skin-based), or tympanic body temperature (eg, Celsius). The Investigator will perform an overall evaluation for safety purposes and the recording will be reported as 'normal', 'abnormal clinically significant (CS)', or 'abnormal not clinically significant (NCS)'.

Criteria of Potentially Clinically Significant Values (PCSV) for Vital⁷

The following criteria to determine risk for PCSV for Vital signs are defined:

HR* at post-baseline ≤ 50 bpm and decrease from baseline ≥ 15 bpm

HR* at post-baseline ≥ 120 bpm and increase from baseline ≥ 15 bpm

SBP at post-baseline ≤ 90 mmHg and decrease from baseline ≥ 20 mmHg

SBP at post-baseline ≥ 180 mmHg and increase from baseline ≥ 20 mmHg

DBP at post-baseline ≤ 50 mmHg and decrease from baseline ≥ 15 mmHg

DBP at post-baseline ≥ 105 mmHg and increase from baseline ≥ 15 mmHg

Note: *HR will be regarded as Pulse Rate.

Orthostatic Hypotension

Orthostatic hypotension will be defined as experiencing lightheadedness and/or dizziness and/or a reduction in systolic BP of 20 mmHg or more, and/or a reduction in diastolic BP of 10 mmHg or more, or increase in heart rate > 20 beats/minute for the standing measurement compared to the supine measurement.

The following criteria to determine "Orthostatic vital sign changes" are defined:

- Decrease of ≥ 20 mmHg from 'Seated (resting 5 minutes)' Systolic Blood pressure to 'Standing (after 1 minute)' Systolic Blood pressure
- Decrease of ≥ 20 mmHg from 'Seated (resting 5 minutes)' Systolic Blood pressure to 'Standing (after 3 minutes)' Systolic Blood pressure
- Decrease of ≥ 10 mmHg from 'Seated (resting 5 minutes)' Diastolic Blood pressure to 'Standing (after 1 minute)' Diastolic Blood pressure
- Decrease of ≥ 10 mmHg from 'Seated (resting 5 minutes)' Diastolic Blood pressure to 'Standing (after 3 minutes)' Diastolic Blood pressure
- Increase of > 20 bpm from 'Seated (resting 5 minutes)' Pulse rate to 'Standing (after 1 minute)' Pulse rate

- Increase of >20 bpm from 'Seated (resting 5 minutes)' Pulse rate to 'Standing (after 3 minutes)' Pulse rate

The Investigator will also evaluate any clinical symptoms due to the orthostatic vital sign changes such as dizziness and lightheadness.

